#### Patient Death While in Study

Finally, we recognize that we are working with a critically ill population that is at risk for death during follow up due to their underlying illness. Before T2 and T3 data collection, the study team will review the EMR to look for records of death, halting all study procedures if death has occurred and noting the date. On phoning any participant, the study team will initiate a conversation to tactfully ascertain the patient’s vital status should a family member answer first. If the patient has died, the study team will provide brief support and their condolences.

#### Withdraw While in Study

If an individual states that they wish to drop out, the study team will respect that as well. A follow-up question may be asked to ascertain the reason for withdraw; however, this is for documentation purposes only.

#### Vulnerable Populations

This project will not enroll individuals from vulnerable populations (e.g., imprisoned persons, minors).

#### Adverse events (AEs), serious adverse events, (SAEs) and unanticipated problems (UPs).

It is recognized that there is a slight risk that some participants may become distressed when completing self-report measures or participating in interviews. When necessary, participants who experience psychological distress *related to completing questionnaires* will be referred for appropriate psychiatric or psychological care. All participants will have access to the PI’s contact information 24 hours a day (shown in the consent form). If a telephone interview is required, a trained study team member who has been trained to be sensitive to the nature of these issues will conduct it.

It is anticipated, in this study, for AEs to be extremely rare as it is a behavioral study. However, it is possible that participants could become distressed in a hospital setting or post-discharge due to increased illness and/or limitations. As such, participants could exhibit signs of and/or experience suicidal ideations or be admitted for mental health symptoms. Therefore, for this study, only increased levels of distress related to completing the questionnaires or completing the coping skills practice and/or suicidal ideations will be considered AEs.

Like, AEs, it is not anticipated that SAEs will occur. However, for this study, an SAE would be defined as a suicide attempt, a hospitalization (post hospitalization that initiated the patient’s eligibility for study

participation), or death. All serious adverse events will be reported within the standard timelines required to the IRB, study sponsor, and/or DSMB, as appropriate and when applicable.

Given the nature of this study, it is anticipated that most enrolled patients will not complete their study visits within the assigned protocol window. Additionally, it is expected that visits and/or mCST practices will be missed. As such, these will not be considered protocol deviations. Should other protocol deviations or unanticipated problems occur, they will be discussed with the PI, documented, and reported to the IRB, study sponsor, and/or DSMB, as appropriate and when applicable.

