## Abbreviations and Definitions

- Adverse Event (AE)
  - Any untoward medical occurrence associated with or observed in the context of a study procedure. For this study and patient population, an AE will be considered any suicidal ideation. No other events will be considered AEs as this patient population is ill and it is expected that other untoward medical occurrences will occur.
- Clinical Trial Management System (CTMS)
  - For this study, a CTMS known as OnCore will be utilized to manage the study's administrative responsibilities and subject level documentation.
- Duke Regional Hospital (DRH)
  - Study site in which eligible patients will be enrolled.
- Duke University Hospital (DUH)
  - Study site in which eligible patients will be enrolled.
- Electronic Data Capture (EDC)
  - For this study, the EDC will be supported by Pattern Health in which relevant study data, such as screening, enrollment, and clinical variables will be documented. Additionally, the study team will utilize RedCap, which is a secure, Duke approved EDC platform, in which the study screening and enrollment logs will be maintained.
- Electronic Health Record (EHR)
  - Used interchangeably with EMR; the EHR is the patient-specific medical record located in the secure MaestroCare (aka: EPIC).
- Electronic Medical Record (EMR)
  - Used interchangeably with EHR; the EMR is the patient-specific medical record located in the secure MaestroCare (aka: EPIC).
- Electronic Patient Reported Outcomes (ePRO)
  - ePRO can be used to describe study source, such as the patient-completed questionnaires (e.g., HADS, PHQ-10, PTSS), or can refer to the system that houses patient-derived data. For this study, ePRO may refer to the patient-questionnaires for psychological distress OR it may refer to the system, which houses the patient-derived data, which is the mCST app known as "Blueprint."
- Hospital Anxiety and Depression Scale survey (HADS)
  - Anxiety and depression symptoms
- Intensive Care Unit (ICU)
  - Defined as any medical, surgical, trauma, neurological, cardiac, or cardio-thoracic unit in which a patient is receiving cardiac or respiratory support for survival means.
- Institutional Review Board (IRB)
  - Ethical and regulatory committee who provides approval and oversight of clinical trial at study site.
- Mobile Coping Skills Training app (mCST, also known as 'Blueprint')

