### 3. Study Design

As mentioned in section 2, this project consists of two distinct aims: aim 1 (usability) and aim 2 (RCT). Aim 1 of this project will be conducted within a population of 5 to 15 healthy volunteers using a single study visit lasting approximately 30 to 60 minutes in which they will be asked to provide feedback on the app and its contents. Individuals enrolled into this aim will be asked to provide feedback via written communication. Feedback will be used to improve the app for Aim 2 (RCT).

Aim 2, which is the main focus of this exploratory pilot randomized clinical trial (RCT) is to be conducted within a population of 60 cardio-respiratory survivors with a 3-month follow-up. Eligible patients will be those individuals who are admitted to the hospital and receive treatment for cardio or respiratory failure. Additional characteristics of the target population are those that exhibit high psychological distress, as defined by their scoring at the time of hospital discharge via the Hospital Anxiety and Depression Scale (HADS) and Post Traumatic Stress Scale (PTSS) surveys. Eligible patients will be identified via daily electronic medical record (EMR) review and approached for consent while still hospitalized. Patients will be

asked to complete app registration and baseline survey completion post-consent, but at the time of hospitalization, if possible. Upon discharge, patients will be asked to complete survey 1, T1, to assess their levels of psychological distress. Should the patient demonstrate high enough levels of psychological distress, they will be randomized to 1 of 3 treatment arms:

- Arm 1: mCST Intervention Group 1 (self-directed coping skills training app with CST therapist intro call)
- Arm 2: mCST Intervention Group 2 (self-directed coping skills training app only)
- Arm 3: usual care (control group; no CST therapist and no coping skills training app)

Each participant, regardless of randomization arm will be asked to complete the following surveys at the listed time points below:

- Baseline (during hospitalization, post consent)
  - Collect sociodemographic data and establish baseline psychological distress.
- T1 (at the time of hospital discharge, within 1 week of returning to home but no more than 1 month (30 days) from discharge)
  - Complete the HADS, PTSS, and PHQ-10, QOL 100-point visual analog scale, IADL/ADLs
- T2 (1 month (30 days) post date of discharge; up to 2 months (60 days) for completion)

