  - Week 3 includes two coping skills: Fast relax and managing negative thoughts. The purpose of fast relax is to help one keep feelings, such as pain or tension levels, low throughout the day by allowing one's self to be still and breath fully for a few seconds to a minute. Managing negative thoughts encourages individuals to understand that having negative thoughts is okay and normal; the practice encourages one to notice their negative thoughts,

such as worry, anger, stress, and then teaches them to take control of the thought(s) and then change the thought to be more positive.

- **Week 4: Problem Solving and Maintenance**
  - *Week 4 includes one additional coping skill: problem solving. Problem solving is a skill that helps an individual focus on one problem at a time and teaches them to 1) recognize what the problem is, 2) understand why there is a problem, and 3) help them think about what they can do to solve the problem. Additionally, during week 4, individuals are instructed on how to maintain the coping skills learned during the previous 3 weeks and are encouraged to practice the skill(s) that worked best for them.*

At the beginning of each week, a brief introduction video explaining the study will be provided. During each week's exercise, patients will have the opportunity to listen to pre-recorded visual audios of physicians and patients describing their own, personal coping mechanisms related to each week's skill.

The native app will track fidelity and adherence by way of automated prompts and the use of an interactive dashboard for administrative users (i.e., study team) to track individual patient use. Should a patient stop responding to the app (e.g., stop using it for any period of time), the study team may contact the patient to remind him/her of their commitment to the study and the importance of compliance.

For those individuals in arm 3, they will receive neither therapist nor app-directed intervention. The study team will administer the weekly surveys during the first month (30 days) via email and/or phone, and at T1, T2, and T3.

The study will be conducted at Duke University Hospital (DUH) and Durham Regional Hospital (DRH).

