#### Characteristics of an Adverse or Serious Adverse Event

#### **Relationship to Study Intervention**

To assess relationship of an event to study intervention, the following guidelines are used:

1. Related (Possible, Probable, Definite)
  - a. The event is known to occur with the study intervention.
  - b. There is a temporal relationship between the intervention and event onset.
  - c. The event abates when the intervention is discontinued.
  - d. The event reappears upon a re-challenge with the intervention.
2. Not Related (Unlikely, Not Related)
  - a. There is no temporal relationship between the intervention and event onset.
  - b. An alternate etiology has been established.

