follow up, and will prepare a report with any recommendations within 2 weeks following their review. The specific study metrics that the DSMB will review at each meeting include enrollment rate, dropout rate, HADS scores, PTSS scores, and Adverse Events. The primary safety measures will be Adverse Events reports and HADS scores.

Other items reviewed by the DSMB at each meeting will include: (a) data quality, completeness, and timeliness; (b) performance of the individual sites; (c) adequacy of compliance with goals for recruitment and retention, including women and minorities; (d) protocol adherence; and (e) presence of factors that could adversely affect study outcome or compromise data confidentiality. Study participants will be recovering from life-threatening illnesses managed in intensive care units, which increase the likelihood of death overtime in comparison to healthy individuals. As such, any patient deaths and their cause during the follow up period will be recorded, discussed, and highly scrutinized.

The study biostatistician will oversee any DSMB statistical requests and interpretations. During the review process, formal statistical tests may be performed under DSMB supervision if requested (e.g., examining the differences in Adverse Event or outcome rates between factor-based groups). Additionally, the DSMB may request a formal statistical assessment if a suspicious increase in HADS score is observed in any factor-based group. If a specific factor group is found to have a statistically significant increase in HADS score, the DSMB scope of action may include recommendation for stopping the trial. For differences in study dropout rates, appropriate changes to the protocol will be made by PI consensus after DSMB member input. Any protocol changes, as well as any adverse events, will also be immediately reported to the relevant site IRB, the Central Institutional Review Board (located at Duke University), as well as to the NHLBI Program Officer.

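### Increased distress is an adverse event only if attributed to questionnaires or coping skills practice; controls have no practice, so the distress part of the AE rate is not comparable between arms

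*Protocol*

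**What the plan says.** **AE definition, safety section.** The protocol's section on AEs, SAEs and unanticipated problems states that "only increased levels of distress related to completing the questionnaires or completing the coping skills practice and/or suicidal ideations will be considered AEs". Shortly before, it recognises that "it is possible that participants could become distressed in a hospital setting or post-discharge due to increased illness and/or limitations". That kind of distress can occur in any arm and is not in the definition. Suicidal ideation counts whatever its cause, and so do the SAEs (suicide attempt, hospitalization, death).

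**AE definition, Abbreviations and Definitions.** This one is narrower: "For this study and patient population, an AE will be considered any suicidal ideation. No other events will be considered AEs".

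**Exposure by arm, Section 3.** "For those individuals in arm 3, they will receive neither therapist nor app-directed intervention". Surveys, in contrast, are common to all: "Each participant, regardless of randomization arm will be asked to complete the following surveys at the listed time points below". The questionnaire route to a distress AE is therefore open in every arm, and the practice route only in Arms 1 and 2.

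**Relatedness.** The protocol has a separate relatedness assessment. Its criteria refer to the study intervention, for example "There is a temporal relationship between the intervention and event onset".

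**Use of the AE data.** Under the DSMB heading, the board's first listed duty is to look for harms of the intervention. "The primary safety measures will be Adverse Events reports and HADS scores". The board may also ask for formal tests, the example given being "examining the differences in Adverse Event or outcome rates between factor-based groups". The term factor-based is not defined. The SAP contains no AE analysis and no AE table.

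**The concern.** An event is normally recorded first and its relationship to treatment judged afterwards. Here part of that judgement decides whether the event is recorded at all, and one of the two qualifying causes cannot apply to a control. Nothing in the documents blinds the person who makes the judgement. The study team itself contacts controls for their weekly surveys, and the group-blinded reports under Data management are for data cleaning.

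Two things follow. If distress that would have occurred anyway is put down to practice, the app-arm rate rises and the control rate cannot. And worsening that nobody connects with a survey or with practice is missing from the AE count in every arm, including worsening in app patients whose link to the app goes unrecognised. At stake is how the DSMB reads AE counts when it judges whether the app does harm.

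**Working it through.** The documents state no AE rate and no power for safety, so there is no figure of the plan's own to reproduce. What follows shows how the distortion depends on attribution. It is an illustration, not an estimate.

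**Inputs**

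- s, chance of suicidal ideation: 5%, assumed. The only anchor is the protocol's remark that fewer than 5% of over 400 earlier participants needed a call from the principal investigator, which is a different event.
- q, chance of increased distress, equal in all arms (no true effect of the app): 10% to 40%, assumed.
- u, share of that distress attributed to questionnaires, any arm: 10%, assumed.
- a, share attributed to practice: 10% to 50% in app arms, assumed; 0 in controls by design. With no true effect, all of a is misattribution.

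**Formulas** (ideation and distress taken as independent)

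- App arms: P(AE) = 1 − (1 − s)(1 − q(u + a))
- Control: P(AE) = 1 − (1 − s)(1 − qu)
- Difference: (1 − s) × q × a. It does not depend on u and is zero when a = 0.

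**Example**, q = 20%, a = 25%: app 1 − 0.95 × (1 − 0.20 × 0.35) = 11.65%; control 1 − 0.95 × (1 − 0.20 × 0.10) = 6.90%; difference 0.95 × 0.20 × 0.25 = 4.75 points.

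| q | a | App arms | Control | Difference (points) |
|---|---|---|---|---|
| 10% | 10% | 6.90% | 5.95% | 0.95 |
| 10% | 50% | 10.70% | 5.95% | 4.75 |
| 20% | 10% | 8.80% | 6.90% | 1.90 |
| 20% | 25% | 11.65% | 6.90% | 4.75 |
| 20% | 50% | 16.40% | 6.90% | 9.50 |
| 40% | 10% | 12.60% | 8.80% | 3.80 |
| 40% | 50% | 27.80% | 8.80% | 19.00 |

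The spurious difference runs from about 1 to 19 points, a ratio of 1.16 to 3.16.

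**If the app truly helps.** Let distress be 20% with the app and 40% in controls, with a = 25%. The recorded AE rates are 11.65% and 8.80%, so the app looks worse. Counting all increased distress gives 1 − 0.95 × 0.80 = 24% against 1 − 0.95 × 0.60 = 43%.

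**With a cause-neutral definition** and equal true distress, every arm has the same rate: 14.5%, 24% and 43% for q = 10%, 20% and 40%. If only suicidal ideation counts, it is 5% in every arm. The definition contributes no difference in either case.

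**Formal test.** Fisher's exact test at two-sided 0.05, over q = 10%, 20%, 40% and a = 10%, 25%, 50%, would reject in 0.3% to 12.2% of trials with 50 app patients against 10 controls (protocol numbers), and in 0.8% to 23.0% with 30 against 15 (SAP numbers). The distortion would mostly show in descriptive rates.

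**The case against.** The case on the other side is substantial, and most of it limits the point rather than removing it.

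- **Biased by definition?** A reader might infer that the whole AE comparison is biased by definition, or that background distress is countable only in the app arms. The documents do not support this. As written, background distress is an AE in no arm, and the relatedness guidance lists an established alternative cause under not related. Bias needs misattribution. Suicidal ideation and questionnaire-related distress can be counted in every arm.
- **Practice-caused distress is real harm.** Only app patients can have it, and counting it there is not an error. This stands.
- **Counting occasions.** A reader might set 28 practice days plus 6 surveys (34 occasions) against 6 surveys for a control and conclude that 28/34 = 82% of the AE opportunity is missing in controls. That is a share of calendar occasions, not of events. To turn it into AE rates one must assume that each practice day is as likely as each survey to produce an attributed AE. The protocol expects practices to be missed and AEs to be very rare.
- **Other monitoring exists.** HADS scores are the other primary safety measure, and a significant HADS increase in a group is the statistical finding that the protocol links to a stopping recommendation. A distress score above the T1 level at T2 or T3 prompts staff contact in any arm. SAEs need no attribution. This limits the consequence, but it does not make the AE rate comparable.
- **The comparison is optional.** Formal tests are run only on request, the groups are undefined, and the DSMB charter, which is not among the documents, is meant to set adverse-outcome definitions. This stands. Review of AEs at each DSMB meeting is not optional, however.
- **The narrower definition removes the asymmetry.** It does, but only by counting no distress at all, including distress caused by practice.

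**Conclusion.** The point holds for one component. The distress part of the AE rate is not like-for-like between arms, because one of its two qualifying causes cannot exist in controls. The text creates the opening; misattribution of background distress by people who may know the arm would create the bias, and its direction would be against the app. Separately, worsening not linked to a survey or to practice is uncounted everywhere.

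The size cannot be derived from the documents. The range of 1 to 19 points rests on the assumed rates of distress and attribution and on equal true distress in all arms; with no misattribution it is zero. No figure in the plan is shown to be wrong, and the documents do not support saying that the DSMB's safety review as a whole is invalid. The point also depends on which AE definition prevails. It is a cheap improvement to a safety measure.

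**What to change.** 1. Reconcile the AE definition in Abbreviations and Definitions with the one in the safety section. This comes first.
2. If distress remains an AE, define it in the safety section without attribution and by the same rule in all arms: a rise in HADS from T1 at the surveys common to all arms, or distress reported at the AE enquiry already planned for each visit. The common surveys are T2, T3 and the weekly HADS, the last once Section 3 (all arms) and note d of Appendix 1 (Arms 1 and 2) agree on whether controls receive it. The size of the rise is for the investigators and the DSMB to set.
3. Record relatedness afterwards as a separate field, using the existing categories.
4. State in the DSMB section, and in the charter, that comparisons of AEs between arms use the cause-neutral count, and that practice-related distress is listed descriptively for Arms 1 and 2.

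The cost is a change of wording. T1 to T3 HADS, the AE enquiry and the relatedness categories already exist, so no new visits or data are needed. The downside is that more AEs will be logged in every arm, most of them background distress.

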#### Period and Frequency for Event Assessment and Follow-Up

Protocol deviations and other unanticipated problems, as well as AEs and SAEs, will be recorded in the data collection system throughout the study and reported, as appropriate, to the IRB, study sponsor, and/or DSMB, when applicable.

The study team will record all reportable events with start dates occurring any time after informed consent is obtained until 7 (for non-serious AEs) or 30 days (for SAEs) after the last day of study participation. At each study visit, the study team will inquire by way of verbal or written request and/or EMR review, of the occurrence of AE/SAEs since the last visit. Events will be followed for outcome information until resolution or stabilization.

#### Characteristics of an Adverse or Serious Adverse Event

#### **Relationship to Study Intervention**

To assess relationship of an event to study intervention, the following guidelines are used:

1. Related (Possible, Probable, Definite)
  - a. The event is known to occur with the study intervention.
  - b. There is a temporal relationship between the intervention and event onset.
  - c. The event abates when the intervention is discontinued.
  - d. The event reappears upon a re-challenge with the intervention.
2. Not Related (Unlikely, Not Related)
  - a. There is no temporal relationship between the intervention and event onset.
  - b. An alternate etiology has been established.

#### **Expectedness**

The Study PI will be responsible for determining whether an event is expected or unexpected. An event will be considered unexpected if the nature, severity, or frequency of the event is not consistent with the risk information previously described for the intervention.

